8.2 Measures to Minimize Bias

8.2.1 Enrollment/Randomization/Masking Procedures

Patients will be randomized (1:1) using REDCap. The physicians and patients will be blinded to their assigned treatment group.

As each patient receives the barbotage, the patient nor the PI will not know if they are receiving the cortisone in addition to the barbotage. Study team members and [name] will not be blinded and in position to randomize the patients. [name] will not be blinded to the study as she is performing the procedures. [name], the PI, and his patients will be blinded from which combination of the two they receive (barbotage and cortisone or saline/sham).

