14	CONFLICT OF INTEREST POLICY	15
15	REFERENCES	17
16	ATTACHMENTS	17

CONFIDENTIAL

This material is the property of the NYU School of Medicine and Langone Medical Center. Do not disclose or use except as authorized in writing by the study sponsor

List of Abbreviations

AE	Adverse Event/Adverse Experience
CFR	Code of Federal Regulations
CRF	Case Report Form
CSOC	Clinical Study Oversight Committee
DCC	Data Coordinating Center
DHHS	Department of Health and Human Services
DSMB	Data and Safety Monitoring Board
FFR	Federal Financial Report
FWA	Federalwide Assurance
GCP	Good Clinical Practice
HIPAA	Health Insurance Portability and Accountability Act
ICF	Informed Consent Form
IRB	Institutional Review Board
ISM	Independent Safety Monitor
MOP	Manual of Procedures
N	Number (typically refers to participants)
NIH	National Institutes of Health
OHRP	Office for Human Research Protections
OHSR	Office of Human Subjects Research
PI	Principal Investigator
QA	Quality Assurance
QC	Quality Control
SAE	Serious Adverse Event/Serious Adverse Experience
SOP	Standard Operating Procedure
US	United States

CONFIDENTIAL

This material is the property of the NYU School of Medicine and Langone Medical Center. Do not disclose or use except as authorized in writing by the study sponsor

Protocol Summary

[figure not shown]
Title	Calcific Tendonitis Treatment-Barbotage vs. Barbotage with Cortisone Injection: A Randomized Controlled Double-Blind Study
Short Title	Calcific Tendonitis Treatment-Barbotage vs. Barbotage with Cortisone Injection
Protocol Number	S19-01299
Population	A sample size of 140 patients belonging to NYU Langone Health with calcific tendonitis will be enrolled including both genders, ages 18-90.
Objectives	The purpose of this study is to determine the efficacy of barbotage therapy by comparing the clinical and sonographic changes in patients that solely receive barbotage to patients receiving the standard of care, barbotage with cortisone injection.
Study Center(s)	Single-center, prospective study
Number of Subjects	We will aim to enroll a total of 140 subjects.
Study Duration	The estimated duration of the study is 24 months.
Subject Participation Duration	Each patient will be present for the day of treatment and follow-up at: 6 weeks, 3 months, and 6 months. Patients will be in the study for 6 months.
Estimated Time to Complete Enrollment	The estimated time to completion of enrollment is 24 months.

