3.2 Study Endpoints

3.2.1 Primary Study Endpoints

The primary study endpoint will focus on the decrease in pain of the affected shoulder measured by VAS scores. Based on their responses and their scores at the time prior to and after their barbotage therapy begins, we can determine a primary endpoint with a 10% change between baseline and their final visit. We would also like to observe the affected rotator cuff tendon and measure the efficacy of barbotage therapy via shoulder radiograph. Shoulder X-Ray is considered standard of care and we expect a resolution in size of the calcified deposit by at least 10% after aspiration and lavage.

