and cortisone/saline (sham) injection will occur concurrently by a different physician from the PI, blinding the PI and patients. The study team members responsible for randomization will converse with the [name], who will be in charge of performing the barbotage and cortisone/saline (sham) procedure. The associated research members and the physician performing the barbotage excluding the PI and patients are the only individuals who will be aware of the blind. Blinding will be maintained until a patient experiences adverse effects, in which case the researchers will inform the primary physician.

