5.2.2 Enrollment/Baseline

Enrollment/Baseline Visit (Visit 1, Day 0)

- Obtain informed consent of potential participant verified by signature on study informed consent form.
- Physical exam
- Randomize into treatment cohort or control cohort
- Schedule follow-up visits
- Record VAS, ASES Shoulder and QuickDASH scores.
- Perform Shoulder Series X-Ray

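### Allocation knowledge is not confined to those who randomise and treat, and nothing requires deposit size on radiograph to be measured by someone masked to arm

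*Combined protocol and SAP*

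**What the plan says.** The title describes the trial as "A Randomized Controlled Double-Blind Study".

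- **Who knows the arm.** Section 8.2.1 states that study team members, with one named person, "will not be blinded and in position to randomize the patients". Of the person who does the barbotage it adds that she "will not be blinded to the study as she is performing the procedures". Section 5.1 says that the associated research members and the physician performing the barbotage "are the only individuals who will be aware of the blind".
- **Who does not.** Sections 5.1 and 8.2.1 say that patients and physicians are blinded. Both then single out the PI and the patients.
- **The radiographic measure.** Section 2.1 includes deposit size on radiograph in the primary objective. Section 3.2.1, under the primary endpoints, plans to "measure the efficacy of barbotage therapy via shoulder radiograph" and expects a reduction of at least 10%. Films are taken at baseline and month 6 (5.1, 5.2.2, 5.2.4, Attachment A).
- **Who handles data.** Section 12.1 gives data collection to the trial staff, supervised by the PI. Section 9 limits access to study records to approved team members. Neither separates masked from unmasked staff.

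**The concern.** Blinding the patient protects what the patient reports. It does not protect a length or area that someone else measures from a film. Deposit size depends on where the reader places its edge, and a reader who knows which patients received cortisone can place that edge differently in the two arms without intending to.

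The section on minimising bias declares the team unblinded in general terms and puts no limit on what an unblinded member may do afterwards. If such a member measured the films, the radiographic comparison could not be defended as blinded. The analysis cannot remove that bias, and a larger sample does not help; the only late remedy is a masked re-read.

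**Working it through.** The plan states no figure on this point, so the check is mainly a comparison of sections.

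**1. Is allocation knowledge limited to those who need it?** Section 5.1 mentions study team members responsible for randomisation, which suggests a subset. Its sentence on who knows the arm, however, refers to the associated research members without that qualifier, and 8.2.1 refers to study team members in general. The text is at best ambiguous. Section 8.2.1 is also inconsistent: it says that physicians are blinded, yet the proceduralist is a physician (5.1) and is unblinded.

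**2. Is the film reader masked?** Sections 2.1, 3.2.1, 5.1, 5.2.2, 5.2.4, 8.1, 8.2.1, 8.2.2, 9, 12.1 and Attachment A cover the endpoint, the timing of films, masking, analysis and data handling. None assigns the measurement to a role or masks the person who makes it. This is not an effect of removed names: no sentence on measuring films has a name taken out. Section 8.1 has protected health information removed before analysis, but that is de-identification and does not hide the arm.

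**3. Which outcomes are exposed?** VAS, ASES and QuickDASH are completed by the patients (5.1), who are blinded. Staff only record them, which is a smaller risk. Deposit size is the outcome that someone other than the patient produces.

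**4. How much could it matter?** This is an illustration, because the documents give no reader-bias figure.

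- Assumption: no true difference between arms, and a difference *b* between arms in mean reading error, in SD units of the outcome.
- Sample sizes: 128/2 = 64 and 140/2 = 70 per arm (8.1).
- Rejection rate of a two-sided 5% z-test: 1 − Φ(1.96 − b/SE) + Φ(−1.96 − b/SE), with SE = √(2/n).
- SE = √(2/64) = 0.177 at 64 per arm and √(2/70) = 0.169 at 70 per arm.

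| b (SD) | b/SE, n = 64 | Rejection rate | b/SE, n = 70 | Rejection rate |
|---|---|---|---|---|
| 0.1 | 0.57 | 8.7% | 0.59 | 9.1% |
| 0.2 | 1.13 | 20.5% | 1.18 | 21.9% |
| 0.3 | 1.70 | 39.6% | 1.77 | 42.7% |

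The error rate is slightly higher at 70 per arm than at 64, so recruiting more patients does not cure it.

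**5. Sensitivity near a 10% change.** On a 5 mm deposit, 10% is 0.10 × 5 = 0.5 mm; on a 10 mm deposit it is 1 mm. A follow-up reading 0.5 mm too large on a 5 mm deposit lowers the apparent reduction by 10 percentage points. It therefore moves a patient below 10% only if the true reduction is at least 10% and under 20%. A deposit that shrinks by 20% or more stays on the same side.

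**The case against.** The strongest reply is that no section gives film measurement to an unblinded person. The sentence in 8.2.1 is about who randomises, 5.1 and 8.2.1 say that physicians are blinded, and 5.1.2 has both arms followed up by their physician. A blinded clinician may well read the films. That stands as a statement about likely practice, and it rules out two stronger readings:

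- A reader might infer that only the PI and the patients are blinded. The wording about physicians does not support that.
- A reader might infer that the films will be read with the arm known. The documents show only that this is permitted.

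The reply does not close the gap, because the task is assigned to nobody and unmasked staff are not excluded from it.

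Other tempting inferences also fail:

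- **That the pain and function scores are compromised.** Blinded patients complete them.
- **That baseline scores follow randomisation.** Section 5.2.2 lists "Randomize into treatment cohort or control cohort" above the scores, but it is a list of activities with no stated sequence, and 5.1 requires scores and film before treatment.
- **That a 0.5 mm reading error reclassifies patients in general.** For films, 10% is worded as an expectation and not as a response rule (3.2.1). The 5 mm entry limit may be met on sonogram instead of radiograph (4.1). The example holds only near a 10% change.
- **That a routine radiology report could serve as the masked reading.** The month-6 film is taken for research (1.3.1, 5.2.4), and no section says that such a report exists or gives deposit size.

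A last objection is that the PI is not a fully secure masked reader. The blind can be broken to the PI after adverse events (5.1, 8.2.2), and the PI's quarterly review includes a comparison of risks between the groups (section 7). This is correct, and the fix allows for it.

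**Conclusion.** The point holds in a limited form. Sections 8.2.1 and 5.1 state, without confining it to those who randomise, that team members know the allocation. Section 12.1 gives data collection to trial staff, and nothing masks whoever measures deposit size. A trial labelled double-blind can therefore comply with its protocol and still have one of its primary measures read with the arm known.

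The exposure is mainly the radiographic measure; the VAS result keeps its protection through patient blinding. The size of any bias cannot be derived from the documents. The rejection rates of about 9%, 20% and 40% at 64 per arm rest wholly on assumed shifts of 0.1, 0.2 and 0.3 SD. They show what is at stake and are not evidence of bias in this trial. Actual practice may be better than the text. This is a cheap improvement, and it does not call the whole trial into question.

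**What to change.** In section 8.2.1, with matching wording in 5.1:

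1. Restrict knowledge of allocation to the randomising team member(s) and the proceduralist, enforced through REDCap user rights, and bar these people from measuring films or entering outcomes.
2. Have baseline and month-6 films measured under study ID, without arm, by the blinded PI or by another existing team member who has no access to allocation.
3. If a patient's blind has been broken to the PI, have another masked team member measure that patient's films.
4. Give the PI between-group safety summaries under masked group labels.
5. Reconcile the statement that physicians are blinded with the statement that the proceduralist is not.

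The cost is protocol wording and a permission setting, using people already on the trial. The downside is slightly less flexible staffing, since those who randomise can no longer enter outcomes and at least one team member besides the PI must stay masked.

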8.2.2 Breaking the Study Blind/Participant Code

The study blind for a single patient will be broken if the patient reports severe adverse events. These events will be recorded and then reported to the PI. The information will be confidentially maintained by the PI and study team members. All information will be protected by REDCap.

9 Source Documents and Access to Source Data/Documents

Source data is all information, original records of clinical findings, observations, or other activities in a clinical trial necessary for the reconstruction and evaluation of the trial. Source data are contained in source documents. Examples of these original documents, and data records include: hospital records, clinical and office charts, laboratory notes, memoranda, subjects' diaries or evaluation checklists, pharmacy dispensing records, recorded data from automated instruments, copies or transcriptions certified after verification as being accurate and complete, microfiches, photographic negatives, microfilm or magnetic media, x-rays, subject files, and records kept at the pharmacy, at the laboratories, and at medico-technical departments involved in the clinical trial.

The study case report form (CRF) is the primary data collection instrument for the study. All data requested on the CRF must be recorded. All missing data must be explained. If a space on the CRF is left blank because the procedure was not done or the question was not asked, write "N/D". If the item is not applicable to the individual case, write "N/A". All entries should be printed legibly in black ink. If any entry error has been made, to correct such an error, draw a single straight line through the incorrect entry and enter the correct data above it. All such changes must be initialed and dated. DO NOT ERASE OR WHITE OUT ERRORS. For clarification of illegible or uncertain entries, print the clarification above the item, then initial and date it.

Access to study records will be limited to IRB-approved members of the study team. The investigator will permit study-related monitoring, audits, and inspections by the IRB/EC, the sponsor, government regulatory

CONFIDENTIAL

This material is the property of the NYU School of Medicine and Langone Medical Center. Do not disclose or use except as authorized in writing by the study sponsor

bodies, and University compliance and quality assurance groups of all study related documents (e.g. source documents, regulatory documents, data collection instruments, study data etc.). The investigator will ensure the capability for inspections of applicable study-related facilities (e.g. pharmacy, diagnostic laboratory, etc.).

Participation as an investigator in this study implies acceptance of potential inspection by government regulatory authorities and applicable University compliance and quality assurance offices.

10 Quality Assurance and Quality Control

QC procedures will be implemented beginning with the data entry system and data QC checks that will be run on the database will be generated. Any missing data or data anomalies will be communicated to the site(s) for clarification/resolution.

Following written SOPs, the monitors will verify that the clinical trial is conducted and data are generated, documented (recorded), and reported in compliance with the protocol, GCP, and the applicable regulatory requirements (e.g., Good Laboratory Practices (GLP), Good Manufacturing Practices (GMP)).

The investigational site will provide direct access to all trial related sites, source data/documents, and reports for the purpose of monitoring and auditing by the sponsor, and inspection by local and regulatory authorities.

11 Ethics/Protection of Human Subjects

11.1 Ethical Standard

The investigator will ensure that this study is conducted in full conformity with Regulations for the Protection of Human Subjects of Research codified in 45 CFR Part 46.

11.2 Institutional Review Board

The protocol, informed consent form(s), recruitment materials, and all participant materials will be submitted to the IRB for review and approval. Approval of both the protocol and the consent form must be obtained before any participant is enrolled. Any amendment to the protocol will require review and approval by the IRB before the changes are implemented to the study. All changes to the consent form will be IRB approved; a determination will be made regarding whether previously consented participants need to be re-consented.

11.3 Informed Consent Process

11.3.1 Consent/Accent and Other Informational Documents Provided to Participants

Consent forms describing in detail the study intervention, study procedures, and risks are given to the participant and written documentation of informed consent is required prior to starting intervention. The consent form is submitted with this protocol.

11.3.2 Consent Procedures and Documentation

Informed consent is a process that is initiated prior to the individual's agreeing to participate in the study and continues throughout the individual's study participation. Extensive discussion of risks and possible benefits of participation will be provided to the participants and their families. Consent forms will be IRB-approved and the participant will be asked to read and review the document. The investigator will explain the research study to the participant and answer any questions that may arise. All participants will receive a verbal explanation in terms suited to their comprehension of the purposes, procedures, and potential risks of the study and of their rights as research participants. Participants will have the opportunity to carefully review the written consent form and ask questions prior to signing. The participants should have the

CONFIDENTIAL

This material is the property of the NYU School of Medicine and Langone Medical Center. Do not disclose or use except as authorized in writing by the study sponsor

opportunity to discuss the study with their surrogates or think about it prior to agreeing to participate. The participant will sign the informed consent document prior to any procedures being done specifically for the study. The participants may withdraw consent at any time throughout the course of the trial. A copy of the signed informed consent document will be given to the participants for their records. The rights and welfare of the participants will be protected by emphasizing to them that the quality of their medical care will not be adversely affected if they decline to participate in this study.

A copy of the signed informed consent document will be stored in the subject's research record. The consent process, including the name of the individual obtaining consent, will be thoroughly documented in the subject's research record. Any alteration to the standard consent process (e.g. use of a translator, consent from a legally authorized representative, consent document presented orally, etc.) and the justification for such alteration will likewise be documented.

11.4 Participant and Data Confidentiality

Information about study subjects will be kept confidential and managed according to the requirements of the Health Insurance Portability and Accountability Act of 1996 (HIPAA). Those regulations require a signed subject authorization informing the subject of the following:

- What protected health information (PHI) will be collected from subjects in this study
- Who will have access to that information and why
- Who will use or disclose that information
- The rights of a research subject to revoke their authorization for use of their PHI.

In the event that a subject revokes authorization to collect or use PHI, the investigator, by regulation, retains the ability to use all information collected prior to the revocation of subject authorization. For subjects that have revoked authorization to collect or use PHI, attempts should be made to obtain permission to collect at least vital status (i.e. that the subject is alive) at the end of their scheduled study period.

Participant confidentiality is strictly held in trust by the participating investigators, their staff, and the sponsor(s) and their agents. This confidentiality is extended to cover testing of biological samples and genetic tests in addition to the clinical information relating to participants. Therefore, the study protocol, documentation, data, and all other information generated will be held in strict confidence. No information concerning the study or the data will be released to any unauthorized third party without prior written approval of the sponsor.

The study monitor, other authorized representatives of the sponsor, or representatives of the IRB may inspect all documents and records required to be maintained by the investigator, including but not limited to, medical records (office, clinic, or hospital) and pharmacy records for the participants in this study. The clinical study site will permit access to such records.

The study participant's contact information will be securely stored at each clinical site for internal use during the study. At the end of the study, all records will continue to be kept in a secure location for as long a period as dictated by local IRB and Institutional regulations.

12 Data Handling and Record Keeping

12.1 Data Collection and Management Responsibilities

Data collection is the responsibility of the clinical trial staff at the site under the supervision of the site PI. The investigator is responsible for ensuring the accuracy, completeness, legibility, and timeliness of the data reported.

All source documents should be completed in a neat, legible manner to ensure accurate interpretation of data. Black ink is required to ensure clarity of reproduced copies. When making changes or corrections,

CONFIDENTIAL

This material is the property of the NYU School of Medicine and Langone Medical Center. Do not disclose or use except as authorized in writing by the study sponsor

cross out the original entry with a single line, and initial and date the change. DO NOT ERASE, OVERWRITE, OR USE CORRECTION FLUID OR TAPE ON THE ORIGINAL.

Copies of the electronic CRF (eCRF) will be provided for use as source documents and maintained for recording data for each participant enrolled in the study. Data reported in the eCRF derived from source documents should be consistent with the source documents or the discrepancies should be explained and captured in a progress note and maintained in the participant's official electronic study record.

Clinical data (including AEs, concomitant medications, and expected adverse reactions data) and clinical laboratory data will be entered into REDCaps. The data system includes password protection and internal quality checks, such as automatic range checks, to identify data that appear inconsistent, incomplete, or inaccurate. Clinical data will be entered directly from the source documents.

